# A. ABBREVIATIONS

The list below includes abbreviations utilized in this template. However, this list should be customized for each protocol (i.e., abbreviations not used should be removed and new abbreviations used should be added to this list).

AE	Adverse Event
ADE	Adverse Device Effect
ANCOVA	Analysis of Covariance
ASADE	Anticipated Serious Adverse Device Effect
CDC	Communicable Disease Center
CIP	Clinical Investigational Plan
CFR	Code of Federal Regulations
CMP	Clinical Monitoring Plan
CONSORT	Consolidated Standards of Reporting Trials
CTA	Clinical Trial Agreement
CRF	Case Report Form
DD	Device Deficiency
EDC	Electronic Data Capture
EC	Ethics Committee
eCRF	Electronic Case Report Forms
FDA	Food and Drug Administration
GCP	Good Clinical Practice
HIPAA	Health Insurance Portability and Accountability Act
ICH	International Conference on Harmonisation
IRB	Institutional Review Board
LOS	Length Of Hospital Stay
LSMEANS	Least-squares Means
MedDRA	Medical Dictionary for Regulatory Activities
NCT	National Clinical Trial
PI	Principal Investigator
SADE	Serious Adverse Device Effect
SAE	Serious Adverse Event
SAP	Statistical Analysis Plan
SOA	Schedule of Activities
SOC	System Organ Class
SOP	Standard Operating Procedure
SSI	Surgical Site Infection
SSO	Surgical Site Occurrence
US	United States
USADE	Unanticipated Serious Adverse Device Event

# **B. REVISION HISTORY**

The table below is intended to capture changes of IRB/EC-approved versions of the protocol, including a description of the change and rationale. A Summary of Changes table for the current amendment is located in the Protocol Title Page. Procedures for amending this protocol can be found in the current SOPs.

Version	Date	Description of Change	Brief Rationale

# 1 Protocol Summary

# 1.1 Protocol Synopsis

Title	A Retrospective Analysis of the Use of Gentrix® Surgical Matrix for	
	Soft Tissue Reinforcement in Ventral Hernia Repair	
Short Title	Gentrix Ventral Hernia Repair study	
Protocol Number	T-GENVIH-002	
Study Description	The purpose of this study is to collect additional safety data and	
	demonstrate the performance of Integra Gentrix® Surgical Matrix for	
	reinforcement of ventral hernia repairs. Retrospective data will be	
	collected and assessed for early post-operative surgical site events	
	and complications in the immediate post-operative period of 90 days.	
Pre/Post-Market	Post-Market	
Product(s)	Gentrix® Surgical Matrix - (6-layer), - Plus (8-layer), and -Thick	
	*Refer to Erreur! Source du renvoi introuvable. at the end of the protocol for product-specific Stock Keeping Units (SKUs) to be included in this study.	
Indications for Use	Gentrix Surgical Matrix is intended for implantation to reinforce soft	
	tissue where weakness exists in patients requiring	
	gastroenterological or plastic & reconstructive surgery.	
	Reinforcement of soft tissue within gastroenterological and plastic &	
	reconstructive surgery includes, but is not limited to, the following	
	open or laparoscopic procedures: hernia (e.g., hiatal/ diaphragmatic)	
	and body wall repair, colon and rectal prolapse repair, tissue repair,	
	and esophageal repair.	
	Gentrix Surgical Matrix minimizes tissue attachment to the device in	
	case of direct contact with viscera.	
Study Design	Single-Arm, Retrospective, Single-Center	
Study Rationale	This study adds to the available data evaluating the safety and	
	effectiveness of Gentrix® Surgical Matrix in ventral hernia repair,	
	particularly in a real-world population.	
L		

Primary Objective	The primary objective of this study is to capture existing clinical		
	performance data to confirm the continued performance of the		
	Gentrix® Surgical Matrix.		
Safety Objective	The safety objective is to capture existing Gentrix® Surgical Matrix		
	Complication data in the immediate post-operative period of 90		
	days.		
	Gentrix® Surgical Matrix Complications are defined but not limited		
	to:		
	Seroma		
	Abscess		
	Dehiscence		
	Hematoma		
	Wound necrosis		
	Ileus		
	Fistula		
Primary Endpoint	Delayed wound healing     Incidence of post-operative complications requiring procedural		
Timary Emapoint	intervention within 90 days post index procedure.		
Secondary	Incidence of early post-operative complications (Surgical Site)		
Endpoints	Occurrences (SSOs)) within 90 days post index procedure (seroma,		
	abscess, dehiscence, hematoma, wound necrosis, ileus, fistula,		
	delayed wound healing).		
	Incidence of Surgical Site Infections (SSIs) within 90 days post		
	index procedure.		
	Incidence of later post-operative complications occurring after 90		
	days post index procedure.		
	4. Incidence of hernia recurrence confirmed by clinical assessment.		
	5. Incidence of reoperation requirement due to index repair.		
Tertiary Endpoints	Average length of hospital stay (LOS) post index procedure		
	(measured in days).		
	2. Rate of opioid usage following procedure as determined by % of		
	prescriptions filled and refilled		
	In a surface and		

Description of Study	The retrospective chart review will include the full consecutive series
Intervention	of patients between 22 years and 80 years old who underwent
	abdominal wall reconstruction for a hernia with Integra Gentrix®
	Surgical Matrix during the time period between November 1, 2017,
	and present (90 days prior).
	Subjects from that consecutive series will be included in the study
	based on the defined inclusion and exclusion criteria.
	Collection of patients' data treated with the Gentrix® Surgical Matrix
	per routine/standard of care use and in accordance with the
	Instructions for Use (IFU).
Study Population	Patients between 22 years and 80 years old (inclusive) at time they
	underwent abdominal wall reconstruction utilizing Gentrix® Surgical
	Matrix as a reinforcement graft during the time period between
	November 1, 2017, and present (90 days prior to the start of the data
	collection).
Inclusion Criteria	1. Patients between 22 years and 80 years old (inclusive) at time
	they underwent abdominal wall reconstruction utilizing Gentrix®
	Surgical Matrix as a reinforcement graft during the time period
	between November 1, 2017, and present (90 days prior to the start
	of the data collection)
	2. Subject underwent abdominal wall reconstruction for a hernia(s)
	using Integra® Gentrix® Surgical Matrix.
Exclusion Criteria	Subject has known allergy to porcine-derived products.
	2. Subject required use of Gentrix® device and a second non-
	Gentrix surgical mesh in the same plane or in different planes for
	single hernia e.g., Gentrix sublay and a synthetic device in the onlay
	position.
	3. Subject had active necrotizing fasciitis or any current known
	uncontrolled systemic infection.
	4. Subject had uncontrolled diabetes, defined as Hb1AC value >7%
	within 12 weeks prior to index procedure.
	5. Subject has been diagnosed with cirrhosis and/or ascites.

Description of Sites/Facilities Enrolling Participants	One site located in the United States (US) will participate in this study.
Study Duration	Approximately three months.
Data Collection Duration	Approximately one month from initiation of the site until data delivery.
Study Visits/Schedule of Study Activities	This retrospective study specifically aims to collect data from the day of the index procedure, and post-operatively up to a maximum of one year or shorter as applicable.
Data Collection	Data will be collected via medical records, study worksheets, and entered into electronic data capture system by the site. The following data will be collected:
	Patient Data:  • Basic demographic data (e.g., gender, year of birth, height,  weight race otheristy picetine and alcohol use history clinical.
	weight, race, ethnicity, nicotine and alcohol use history, clinical presentation, diagnosis, and relevant medical history up to 3 years prior to surgery).
	Procedural Data:
	Index Surgery:
	
 
Ventral Hernia Details: Location and size of the ventral hernia(s), CDC Wound Class (the highest one) and complications associated with Hernia(s) repair.
 
Surgery Details: Surgical approach (Robotic, Laparoscopic, Robotic assisted, Laparoscopic assisted, MIS converted to open, Open), Times related to the different steps of the index surgery.
 
Type of the Gentrix Surgical Matrix Used.
 
Intraoperative Details: Surgical Plane of graft placement, Graft fixation, Component separation, Concomitant procedure, Stoma presence, and Fascial closure.
 

	Clinical Performance and Safety Evaluation:
	Post operative complications

	2. SSI(s)
	3. Hernia recurrence
	4. Hospital re-admission(s)
	5. Reoperation(s)
	6. Device Deficiency(ies)
	7. Adverse Event(s)
	8. Concomitant medications
	9. Opioid usage following procedure
Statistical Methods	Study outcomes will be summarized using descriptive statistics.
& Analyses	Categorical variables will be summarized using frequencies and
	percentages. Continuous variables will be summarized using means,
	standard deviations, medians, quartiles, ranges, and numbers of
	observations.
	Statistical analysis will be based on data from all evaluable subjects
	meeting the eligibility criteria. Subgroup analyses may be performed
	for surgical approach and type of the Gentrix Surgical Matrix Used.
	1

# 1.2 Schedule of Data Collection Activities

#### **Table 1: Scheduled of Data Collection Activities**

Retrospective Data Collection	Screening	Index Surgery	Discharge	Follow-up Visit
Eligibility	Х			
Demographics	X			
Medical history	Х			
Ventral hernia details (location, size)		Х		
CDC Wound Class (highest applicable class)		Х		
Complications associated with Hernia(s) repair		Х		
Surgery details (surgical approach, Time into procedure room, Time skin cut, Time skin closed, and Time out of procedure room)		X		
Gentrix Surgical Matrix Used (type)		Χ		
Intraoperative Details (Surgical Plane of Graft Placement, Graft fixation, Component Separation, Concomitant Procedure, Stoma presence (if applicable), Fascial closure)		Х		
Adverse events		Χ	Х	Χ
Device deficiencies		Х		
Concomitant medication		Х	Х	Χ
Complete Case Report Forms (CRFs)	Х	Х	Х	Х

# 2 Introduction

# 2.1 Background

Ventral hernias are a type of abdominal hernias that can occur at any location along the vertical abdominal wall. Typically, these defects are acquired resulting from complications of a prior surgery, trauma or natively weak points of the abdominal wall in some individuals. Obesity may contribute in large part to the weak points due to cyclic patterns of weight gain and loss. One in 8 patients will develop an incisional hernia after abdominal surgery.

Ventral hernia repair is one of the most common surgical procedures performed in the United States. Every year there are approximately 350,000 repairs performed in the US with an estimated cost of \$3.2 billion. Different patient populations require different solutions in order to make a repair as cost-effective and risk-averse as possible.

Clinical evidence has shown that primary suture repair of a ventral hernia alone results in high recurrence rates (>50%), and that all incisional hernia repairs should be reinforced with surgical mesh. Despite this consensus, due to the large variety of surgical meshes available currently, there is a lack of consensus on the ideal material for each repair. Ventral hernia treatment decisions are typically tied to patient operative risk, symptomatic concerns and potential clinical complications of the repair.

Permanent synthetic mesh has been the standard of care in the reinforcement of simple, clean hernias due to its minimal cost and history of low recurrence. However, due to the inherent permanence, long-term complications such as product migration, contraction, erosion, and infection are common. In the complex hernia setting, synthetic materials may not be ideal due to the increased risks of surgical site occurrences (SSOs) and resulting recurrences. These complications can prove costly with each hernia recurrence and wound event estimated to cost an additional \$44,000 and \$85,000 respectively. Specifically, a mesh infection can cost up to \$140,000 and may require explanation of the mesh altogether.

Biologically-derived materials, such as acellular dermal matrices, were developed for use in complex hernia repair to mitigate some of the risks seen with synthetic materials. However, long-term study of these materials demonstrated a 31.8% recurrence rate and 36.6% wound infection rate at 18.2 months follow-up.

Approximately 74% of inpatient ventral hernia repairs are completed as open procedures. While this number is slightly lower for outpatient ventral hernia repairs (64%), this remains the predominant surgical approach likely for more complex cases.

#### **Integra LifeSciences**

Currently available biologically derived mesh options for reinforced repairs include a class of nondermal products including Gentrix Surgical Matrix devices.

This post-market clinical study is being conducted to characterize the performance and safety of Gentrix® Surgical Matrix -(6-layer), -Plus (8-layer) and -Thick devices in the repair of ventral hernias in patients between 22 years and 80 years old (inclusive) at time they underwent abdominal wall reconstruction utilizing Gentrix Surgical Matrix as a reinforcement graft during the time period between November 1, 2017, and present (90 days prior).

# 2.2 Investigational Product Overview

Gentrix Surgical Matrix is intended for implantation to reinforce soft tissue where weakness exists in patients requiring gastroenterological or plastic & reconstructive surgery. Reinforcement of soft tissue within gastroenterological and plastic & reconstructive surgery includes, but is not limited to, the following open or laparoscopic procedures: hernia (e.g., hiatal/diaphragmatic) and body wall repair, colon and rectal prolapse repair, tissue repair, and esophageal repair. Gentrix Surgical Matrix minimizes tissue attachment to the device in case of direct contact with viscera.

The Gentrix Surgical Matrix Device configuration includes the Gentrix Surgical Matrix (6-layer), Gentrix Surgical Matrix Plus (8-layer), and the Gentrix Surgical Matrix Thick.

#### 2.2.1 Gentrix Surgical Matrix (6-layer):

Gentrix™ Surgical Matrix (6-layer) is composed of a porcine-derived extracellular matrix, also known as urinary bladder matrix. The device is supplied in a multilayer sheet configuration in sizes up to 10 cm x 15 cm and packaged in double peel-open pouches. The device is terminally sterilized using electron beam irradiation.

[figure not shown]

Figure 1: Gentrix™ Surgical Matrix (6-layer)

# 2.2.2 Gentrix Surgical Matrix Plus (8-layer):

Gentrix™ Surgical Matrix Plus (8-Layer) is composed of porcine-derived extracellular matrix, also known as urinary bladder matrix. The device is supplied in a multilayer sheet configuration in sizes up to 10 cm x 15 cm and packaged in double peel-open pouches. The device is terminally sterilized using electron beam irradiation.

Figure 2 : Gentrix™ Surgical Matrix Plus (8-layer)

#### 2.2.3 Gentrix Surgical Matrix Thick:

Gentrix™ Surgical Matrix Thick is composed of a porcine-derived extracellular matrix, also known as urinary bladder matrix. The device is supplied in a multi-layer sheet configuration in sizes up to 30 cm x 40 cm and packaged in double peel-open pouches. The device is terminally sterilized using electron beam irradiation. Animal studies have shown device resorption in approximately 240 days.

Figure 3 : Gentrix™ Surgical Matrix Thick

#### 2.2.1 Study Device Intended Purpose

The Gentrix Surgical Matrix Devices were used within label in this retrospective study. There were no specific medical or surgical procedures involved in the use of the study devices, other than the standard of care. A full description of the medical and surgical procedures related to the Gentrix Surgical Matrix Devices is available in the Instructions for Use.

#### 2.2.2 Study Device Contraindication

Patients with known sensitivity or allergy to porcine materials.

#### 2.2.3 Required Training and Experience

Previously trained on the use of the devices, the investigator must have used the devices within label in this study. Integra LifeSciences Corporation did not train, nor dictate, the surgery

**Integra LifeSciences** 

INTEGRA

technique(s). The investigator must meet certain expectations per Sponsor Standard Operating Procedures (SOPs).

## 2.2.4 Device Accountability

Given the retrospective data collection of this study, no device accountability will be performed for the purposes of this study.

#### 2.2.5 Device Traceability

Devices will be tracked by type, size, and lot numbers, as applicable, which will be part of the data entered into the database of this retrospective study.

## 2.3 Study & Design Rationale

This is a single-arm, single-center, retrospective study to collect in routine use additional safety data and demonstrate the performance of Integra Gentrix® Surgical Matrix for reinforcement of ventral hernia repairs. Routine use data between November 1, 2017, and present (90 days prior) will be collected retrospectively at 1 site. This study adds to the available data evaluating the safety and effectiveness of Gentrix Surgical Matrix in ventral hernia repair, particularly in a real-world population.

# 3 Objectives and Endpoints

#### 3.1 Primary Objective

The primary objective of this study is to capture existing clinical performance data to confirm the continued performance of the Gentrix® Surgical Matrix.

Existing clinical data support the safety and performance of the Gentrix® Surgical Matrix. There are currently no safety concerns with these products. This clinical investigation will confirm the safety and performance of the Gentrix® Surgical Matrix and identify any unknown side-effect.

#### 3.2 Safety Objective

The safety objective of this study is to capture existing Gentrix® Surgical Matrix Complication data in the immediate post-operative period of 90 days.

Gentrix® Surgical Matrix Complications are defined but not limited to:

- Seroma
- Abscess
- Dehiscence

#### **Integra LifeSciences**

- Hematoma
- Wound necrosis
- Ileus
- Fistula
- Delayed wound healing

# 3.3 Primary Endpoint

The primary endpoint of this retrospective study is the incidence of post-operative complications requiring procedural intervention within 90 days post index procedure.

#### 3.4 Secondary Endpoints

- 1. Incidence of early post-operative complications (Surgical Site Occurrences) within 90 days post index procedure (seroma, abscess, dehiscence, hematoma, wound necrosis, ileus, fistula, delayed wound healing).
- 2. Incidence of Surgical Site Infections (SSIs) within 90 days post index procedure.
- 3. Incidence of later post-operative complications occurring after 90 days post index procedure.
- 4. Incidence of hernia recurrence confirmed by clinical assessment.
- 5. Incidence of reoperation requirement due to index repair.

# 3.5 Tertiary Endpoints

- 1. Average length of hospital stay (LOS) post index procedure (measured in days).
- 2. Rate of opioid usage following procedure as determined by % of prescriptions filled and refilled.

# 4 Study Design

#### 4.1 Overall Design

The Gentrix Ventral Hernia Repair study is a single-arm, retrospective, single-center, post-market study.

# 4.2 Scientific Rationale for Study Design

This study adds to the available data evaluating the safety and effectiveness of Gentrix Surgical Matrix in ventral hernia repair, particularly in a real-world population.

# 4.3 End of Study Definition Overview

The end of the study is defined as completion of Case Report Forms (CRFs) for the last subject in this retrospective study.

# 5 Study Population

#### 5.1 Inclusion Criteria

- 1. Patients between 22 years and 80 years old (inclusive) at time they underwent abdominal wall reconstruction utilizing Gentrix® Surgical Matrix as a reinforcement graft during the time period between November 1, 2017, and present (90 days prior to the start of the data collection).
- 2. Subject underwent abdominal wall reconstruction for a hernia(s) using Integra® Gentrix® Surgical Matrix.

#### 5.2 Exclusion Criteria

- 1. Subject has known allergy to porcine-derived products.
- 2. Subject required use of Gentrix® device and a second non-Gentrix surgical mesh in the same plane or in different planes for single hernia e.g. Gentrix sublay and a synthetic device in the onlay position.
- 3. Subject had active necrotizing fasciitis or any current known uncontrolled systemic infection.
- 4. Subject had uncontrolled diabetes, defined as Hb1AC value >7% within 12 weeks prior to index procedure.
- 5. Subject has been diagnosed with cirrhosis and/or ascites.

#### 5.3 Description of the site

One site in the USA will be selected to participate in this study. The study site will be selected based upon their experience with the subject device, their clinical expertise, expected commitment to have available data for eligible study patients, and their ability to fulfill general requirements in the Sponsor's SOPs and to comply with this protocol.

#### 5.4 Point of Enrollment & Enrollment Period

There are no physical participants as this is a retrospective study. The requirement for consent being waived, the patients will not provide informed consent to allow use of their data. There is no traditional enrollment period in this study. Data will begin to be collected from the first patient who meets all the eligibility criteria.

This study is anticipated to have a data collection period of one month from initiation of the site until data delivery.

The total expected duration of the study is, therefore, approximately 3 months.

#### 5.5 Screen Failures

Screen failures are defined as subjects created by the site on the Case Report Form (CRF) who do not meet one or more eligibility criteria for participation in the study. A minimal set of screen failure information is required to ensure transparent reporting of screen failure participants, to meet the Consolidated Standards of Reporting Trials (CONSORT) publishing requirements and to respond to queries from regulatory authorities. Minimal information to be collected on the CRF includes demography, screen failure details, eligibility criteria, and any serious adverse event (SAE). This will be documented on the Screening and Enrollment log.

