# 6 Study Assessments and Procedures

#### 6.1 Schedule of Data Collection

### 6.1.1 Screening

- The procedures to be completed are:
  - ✓ Retrospective chart review will include the full consecutive series of patients between 22 years and 80 years old who underwent abdominal wall reconstruction for a hernia with Integra Gentrix® Surgical Matrixbetween November 1, 2017, and present (90 days prior).
  - ✓ Creation on the eCRF of a new case book for each eligible subject. Each created case book assigns the eligible subject with a study number.
  - ✓ Completion of Worksheets/ eCRFs: Site will transcribe/transmit the below-mentioned patients' data in study worksheets & eCRFs. The patients' data will originate from existing medical and other patient records.
- The patients' data to be collected are:
  - ✓ Eligibility:
    - o Inclusion Criteria: Ensure the subject meets the inclusion criteria.
    - o Exclusion Criteria: Ensure the subject does not meet any of the exclusion criteria.
  - ✓ Demographics: gender, year of birth, height, weight, race, ethnicity, nicotine and alcohol use history.
  - ✓ Medical history: Obtain subject 's medical history up to 3 years prior to surgery. Medical history is considered relevant when related to any of the study eligibility criteria, or when it may affect any of the clinical investigation endpoints, at the discretion of the investigator. Relevant medical history covers at a minimum Ventral Hernia related medical history treated in this study.

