#### **10.3 Populations for Analyses**

**Full Analysis set (FAS):** All subjects who enroll in the study, provide informed consent waiver, and receive study intervention.

**Per-Protocol (PP) Set:** All subjects in the full Analysis Set not identified as major protocol violations (defined to be protocol violations that may have a significant impact on subject outcomes, i.e., eligibility criteria not met). This population will be clearly defined prior to data analysis.

The primary analysis will be based on the full analysis set. The per-protocol set will be supportive and will be used to assess the robustness of study results. Safety analysis will be based on the full analysis set.

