#### 6. PROTOCOL DEVIATION

Protocol violations will be tracked by the study team throughout the conduct of the study. Data will be reviewed prior to closure of the database to ensure all important violations are captured and categorized.

A major protocol deviation is any significant protocol deviation that threatens the scientific validity of the data collection for a subject or is a serious violation of ethical study compliance and GCP. Examples of major protocol deviations include but are not limited to the following:

• Violation of inclusion/exclusion criteria at enrollment

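### Do the differing rules for a case-book patient who fails an eligibility criterion undermine the analysis sets?

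*Protocol*

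**What the plan says.** - Protocol 5.5: "Screen failures are defined as subjects created by the site on the Case Report Form (CRF) who do not meet one or more eligibility criteria". A minimal data set is required for them (demography, failure details, criteria, SAEs), recorded on a screening and enrolment log.
- Protocol 6.1.1 lists, among the screening steps, "Creation on the eCRF of a new case book for each eligible subject" and adds "Each created case book assigns the eligible subject with a study number".
- Protocol 5.4: "There is no traditional enrollment period in this study". It also says data collection starts with the first patient who satisfies every criterion.
- Protocol 10.3 forms the per-protocol set by removing major violations from the full analysis set, defining them as "protocol violations that may have a significant impact on subject outcomes, i.e., eligibility criteria not met". It continues: "The primary analysis will be based on the full analysis set". On the other set it says: "The per-protocol set will be supportive and will be used to assess the robustness of study results". It promises a clear definition of the per-protocol population before analysis.
- SAP 6 gives one example of a major deviation, "Violation of inclusion/exclusion criteria at enrollment", in a list it calls non-exhaustive. It also requires violations to be reviewed and categorised before the database closes.
- SAP 7 defines the enrolled population as the eligible subjects, draws ITT from it, and uses the per-protocol set only if needed.
- SAP 9.2.1 reports screen-failed and enrolled subjects as separate counts.
- The Protocol synopsis ties the analysis to evaluable subjects who satisfy the eligibility criteria.

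**The concern.** Every candidate has already been operated on and consent is waived, so no visit or signature separates screening from enrolment. A subject with a case book who fails a criterion can be read as non-existent (6.1.1), as a screen failure (5.5), as an analysed subject with a major violation (10.3, SAP 6), or as outside ITT (SAP 7).

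The situation is realistic. Charts are selected by hand (Protocol 5.6), some exclusions depend on chart detail, and full source verification takes place at one visit after the eCRFs are complete (Protocol 6.3). A failed criterion could therefore surface when outcomes are already entered.

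Two things would be at stake: who is in the primary denominator, and whether the ITT versus per-protocol comparison, the only planned robustness check, carries any information.

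**Working it through.** The plan states no figure that depends on this point. The 35 subjects in Protocol 10.2 and SAP 8 are a planned count without a formula. The check is therefore set logic, followed by an illustration of scale.

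**1. Set logic.** Take 35 case books, of which k fail a criterion (k is assumed).

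| Reading | Screen failed | Primary set | Per-protocol, on eligibility |
|---|---|---|---|
| 5.5 with SAP 7 | k | 35 − k | 35 − k |
| 10.3 with SAP 6, all k kept as enrolled | 0 | 35 | 35 − k |
| Customary: s found at screening, v found after enrolment, s + v = k | s | 35 − s | 35 − s − v = 35 − k |

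A strict reading of 6.1.1 together with SAP 7 makes k = 0, and both outputs are then empty.

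In the first row the eligibility-based comparison is empty. In the second row the screen-failed count is empty. In the third row both can be filled. The last column is the same throughout: the eligible-only result is either the primary result or the per-protocol one. What changes is its label.

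**2. How firmly the text imposes the strict readings.**
- 6.1.1 asks for a case book for each eligible subject. It does not say that nobody else may have one, and the same section records the criteria as data.
- 10.3 removes ineligible subjects from the full analysis set. This implies that some may be in it; it does not say that every ineligible case-book subject is.
- 5.5 asks for minimal data and no endpoints, which fits a failure caught at screening. Table 1 places eligibility in the screening column.
- SAP 6 refers to violations at enrolment, and SAP 9.2.1 counts screen failed and enrolled separately.

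These passages fit the customary reading. Two do not: the enrolled definition in SAP 7 and the synopsis, both of which restrict the analysis to eligible subjects.

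**3. Scale.** Let e be the number of primary events among the 35 (assumed). With the k subjects kept, the proportion is e/35. With them removed, it is (e − k)/(35 − k) if all k had the event, or e/(35 − k) if none did.

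| k | e | Kept | Removed, all had event | Removed, none had event |
|---|---|---|---|---|
| 1 | 4 | 4/35 = 11.4% | 3/34 = 8.8% (−2.6) | 4/34 = 11.8% (+0.3) |
| 1 | 7 | 7/35 = 20.0% | 6/34 = 17.6% (−2.4) | 7/34 = 20.6% (+0.6) |
| 1 | 11 | 11/35 = 31.4% | 10/34 = 29.4% (−2.0) | 11/34 = 32.4% (+0.9) |
| 3 | 7 | 7/35 = 20.0% | 4/32 = 12.5% (−7.5) | 7/32 = 21.9% (+1.9) |

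For comparison, the exact 95% interval for 7/35 runs from 8.4% to 36.9%, a width of 28.5 points.

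**The case for a change.** The best case for acting is that the customary reading is written nowhere. Section 5.5 sets no time limit, 5.4 is headed as the point of enrolment but fixes none, and SAP 7 contradicts the convention. The SAP, which should have settled the per-protocol set, refers to a full analysis set it never defines. SAP 9.3.5 places safety in the enrolled population and also in the full analysis population, while SAP 7 says ITT. A late failure would be classified by people who can see the outcomes, and the pre-lock review in SAP 6 controls the timing of that choice without blinding it. One sentence would settle the matter.

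The textual part stands: the definitions are not aligned, and no timing rule is given. The need for an amendment does not follow. A rule keeping late-found failures in the primary set would contradict the synopsis and SAP 7. In a retrospective chart review, where no randomised comparison needs protecting, counting ineligible charts in the primary proportion is itself debatable. The opposite rule would only confirm what the synopsis and SAP 7 already say. Both options are defensible, and neither would make the reported proportion more valid. The open-outcome risk is limited because eligibility is checked against source records, and Protocol 10.4.1 and 10.4.10 call for listings of all collected data, so a reclassified subject would be visible.

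**Conclusion.** The inconsistency is real but no change to the plan is needed. Analysts can fill the gap with the usual convention when violations are categorised before database closure, a step both documents already provide for. There is no hypothesis or threshold (Protocol 10.1, SAP 9.1), so no conclusion turns on the choice. Each reading yields a sound descriptive proportion for a describable group.

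One reclassified subject moves the primary percentage by 0.3 to 2.6 points for assumed totals of 4 to 11 events. The 7.5-point shift requires three ineligible subjects, all with events. The conclusion rests on few or no such subjects being found, a number the documents do not give, and on the report stating how any that are found were handled. An empty eligibility-based per-protocol comparison would mean only that the primary set was already restricted to eligible subjects; SAP 6 leaves room for other grounds of deviation.
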